### Data analysis

Analyses for causal inference regarding primary, secondary and safety outcomes will employ a quasi-experimental method called *difference-in-difference* (DID) analysis to control for secular trends and confounding of unknown individual factors associated with the outcome of interest. The DID approach will provide an estimate of the effect of the Code Sepsis intervention on primary, secondary, and safety outcomes by comparing the intervention and control hospitals during the pre- and post-implementation periods (Figure 1).

For the primary outcome, DID analysis will use multivariable linear regression to compare the adjusted mean door-to-

antibiotic time (primary outcome) at the intervention hospital

pre- versus post-implementation of the Code Sepsis protocol using the measured change at contemporaneous control non-intervention hospitals to control for pre-/post-intervention changes not attributable to protocol implementation after adjustment for potential confounders.

The following equation will be used to estimate the adjusted mean differential change in the primary outcome, door to antibiotic time:

$$Y_{igt} = \beta_0 + \beta_1 Int_g + \beta_2 Post_t + \beta_3 (Int_g * Post_t) + \beta_4 Cov$$

Where  $Y_{igt}$  is the door-to-antibiotic time for patient *i* treated at an intervention or non-intervention ED *g* at pre- or post-intervention time *t*. *Int* is a binary indicator for the subject being treated at an intervention hospital; *Post* is a binary indicator the post-intervention period; and *Cov* represents a vector of patient-level covariates. The  $\beta_3$  parameter from the regression model presented above estimates the adjusted mean differential change in door-to-antibiotic time observed in the Code Sepsis intervention hospital compared to the control hospital. We will consider the Code Sepsis intervention to have had an impact if  $\beta_3$  is statistically significant and different from zero.

The parallel trend assumption will be tested using the approach outlined by Callaway and Sant'Anna. This approach allows for testing the parallel trend assumption after conditioning on covariates. This approach is

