limited in that it only considers the control and treated groups during the pre-implementation phase. If the pre-test of parallel trends assumption fails, then we will weight the gamma regression model with propensity scores. As demonstrated by Stuart *et. al*, this will balance the covariates amongst the four study groups defined by their treatment status as well as time (pre vs post). We will leverage the covariate balancing propensity score (CBPS) library in R to generate propensity scores. This weighting approach can recover treatment effects in that it allows for adjustments due to observed baseline covariates that differ either across groups or over time. Covariates that will be used in generating propensity scores will include age; sex; weighted Elixhauser comorbidity score; English language preference; first-available heart rate, temperature, systolic blood pressure, and respiratory rate; acute physiology score; ED arrival at nightime (10 pm to 6:59 am), ED arrival on weekend (midnight Saturday to 11:59 pm Sunday), SARS-CoV-2 test result (positive, negative, or not performed during ED-associated hospitalization or within 14 days preceding ED arrival); and insurance type. For analyses involving a cohort of patients with sepsis, propensity score covariates will additionally include arrival to ED via ambulance; presentation from a long term care facility; serum lactic acid level checked and ≥2 mmol/dL; ED SOFA score; and ED-diagnosed infection source.

In order to account for the right skew known to exist in door-to-antibiotic time we will use generalized linear gamma regression to estimate the DID. Evaluation of secondary outcomes will employ an analogous approach using multivariable linear, Poisson, logistic, or gamma regression as appropriate. Data from the wash-in phase will be excluded from DID analyses. All multivariable models will be adjusted for demographic and clinical parameters with known or plausible associations with both outcomes and treatment hospital, presentation before or after Code Sepsis implementation, and/or Code Sepsis activation as well as select precision variables as detailed below. Analyses for secondary, safety, and heterogeneity of treatment effect outcomes will not be adjusted for multiple comparisons and will therefore be considered hypothesis generating.

Statistical significance will be set to p < 0.05. All analyses will be conducted with R.

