#### Sensitivity analyses

*Key sensitivity analysis*: To augment causal inference from the primary analysis and evaluate for the possibility of non-parallel trends in the primary outcome at intervention versus control hospitals during the preintervention phase, we will perform a sensitivity analysis evaluating the adjusted primary outcome (door-toantibiotic time) with a multi-group interrupted time series analysis. The following segmented regression suggested by Ryan et.al. will be used to estimate the effect of the Code Sepsis intervention on door-toantibiotic time:

$$Y_{igt} = \beta_0 + \beta_1 Time + \beta_2 (Time * Int_g) + \beta_3 Post_t + \beta_4 (Int_g * Post_t) + \beta_5 Cov$$

Where  $Y_{igt}$  is the door-to-antibiotic time for patient *i* treated at an intervention or non-intervention ED *g* at pre- or post-intervention time *t*. *Time* is a continuous variable indicating the bi-weekly count from the start of the observation period; *Int* is a binary indicator for the subject being treated at an intervention hospital; *Post* is a binary indicator for the post intervention period. The  $\beta_4$  parameter from the regression model is interpreted in nearly the same manner as the primary outcome, in that it estimates the adjusted differential change in door-to-antibiotic time between the control and CodeSepsis hospitals. This model allows for the trends to differ between the intervention and control hospitals during the pre-intervention phase. We will consider the Code Sepsis intervention of have had an impact if  $\beta_4$  is statistically significant and different from zero.

In order to account for the right skew known to exist in door-to-antibiotic time we will use generalized linear gamma regression to estimate the DID. Data from the wash-in phase will be excluded from the sensitivity analysis.

- Other primary outcome sensitivity analyses:
  - Repeat primary analysis among patients in "sepsis high-risk" cohort who received antibiotics in the ED.
  - Repeat primary analysis in the dataset comprising all *encounters* (≥1 encounter per patient) meeting sepsis criteria between ED arrival and ED departure, using generalized linear models with a random effect for patient to account for non-independence.
  - $\circ$   $\,$  Missing data sensitivity analyses as described in the "Missing Data" section  $\,$

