### Power

It was estimated that the intervention ED provides care for 1,650 sepsis patients annually (approximately 4.5 sepsis patients per day) and the control EDs together care for a total of 2,200 sepsis patients annually (approximately 6 sepsis patients per day). Estimated control door-to-antibiotic time for ED sepsis patients was an average 170 (±75) minutes based on 2013-2017 data from study hospitals, with approximately 5-10% of patients receiving antibiotics within 1 hour of ED arrival. Based on these assumptions, we estimated 90% power to detect a difference-in-differences change of 16 minutes or more in door-to-antibiotic time associated with Code Sepsis implementation, with the measurement population being all ED sepsis patients. Power calculations employed Monte Carlo simulations.

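### The primary test specifies no variance for hospital-by-time variation; fitted as written, its standard error assumes independent patients and is too small if hospitals drift separately

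*SAP*

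**What the plan says.** The SAP's Data analysis section models door-to-antibiotic time per patient on a treated-hospital indicator, a post-period indicator, their interaction (β3) and patient-level covariates. It introduces the analysis as linear regression and then specifies a gamma generalized linear model because of right skew. The rule is: "We will consider the Code Sepsis intervention to have had an impact if" β3 "is statistically significant and different from zero", and "Statistical significance will be set to p < 0.05". The two control hospitals share one indicator.

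No variance estimator is named in either document. There is no hospital-by-time term, no clustered or bootstrap variance, and no intraclass correlation. The only stated allowance for correlated observations is in the Sensitivity analyses section, for the dataset of all encounters, "using generalized linear models with a random effect for patient to account for non-independence".

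The Power section supplies the planning figures: "the intervention ED provides care for 1,650 sepsis patients annually", "the control EDs together care for a total of 2,200 sepsis patients annually" and "Estimated control door-to-antibiotic time for ED sepsis patients was an average 170 (±75) minutes". It concludes that "we estimated 90% power to detect a difference-in-differences change of 16 minutes or more in door-to-antibiotic time". The analysis uses one year before and one year after, without the wash-in.

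**The concern.** Patients treated in the same ED in the same weeks share its staffing, crowding and physicians. The protocol gives reasons to expect this to matter. Its Background reports that ED busyness went with delayed antibiotics and that physicians differed five-fold in median door-to-antibiotic time. Its Setting section says that other physician groups staff the control EDs. Census, patient flow and staffing are among the collected variables, but none is in the SAP's covariate list for the primary outcome.

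If one hospital has good or bad months that the others do not, the patient-level standard error of β3 does not include that variation. The nominal 5% test then rejects too often, and a favourable stretch at the intervention ED could be declared an effect of Code Sepsis. The stake is practical: the protocol's Study Overview expects continuation or wider adoption to depend on these analyses.

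**Working it through.** **Inputs.** From the SAP's Power section: 1,650 sepsis patients per year at the intervention ED, 2,200 at the two control EDs together, SD 75 minutes. From the study phases: one year pre and one year post, so N = 2 × (1,650 + 2,200) = 7,700. Assumed, because the documents give no value: the SD τ of hospital-specific monthly shocks.

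**Step 1. The plan's own power figure.** With independent patients,

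SE = 75 × √(2/1650 + 2/2200) = 3.45 min.

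Power at 16 minutes is Φ(16/3.45 − 1.96) = 99.6%, and the effect detectable with 90% power is 11.2 minutes. The stated 90% at 16 minutes is therefore not reproduced from its written inputs. It is reproduced (90.6%, SE 4.885) if 1,650 and 2,200 are totals over both periods, that is 825 and 1,100 per period, still with independent patients.

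**Step 2. Add hospital-month shocks.** There are 12 treated and 24 control hospital-months per period. Independent shocks add τ² × (2/12 + 2/24) = 0.25τ² to the variance of the estimate. The written test still uses 3.45, so

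true type I error = 2 × [1 − Φ(1.96 × 3.45 / √(3.45² + 0.25τ²))].

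| τ (min) | True SE | Type I error | Power at 16 min with the true SE |
|---|---|---|---|
| 0 | 3.45 | 5.0% | 99.6% |
| 1 | 3.49 | 5.2% | 99.6% |
| 2 | 3.60 | 6.0% | 99.4% |
| 3 | 3.77 | 7.2% | 98.9% |
| 5 | 4.26 | 11.2% | 96% |
| 10 | 6.08 | 26.5% | 75% |

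For scale, τ = 5 is 25/5625 = 0.4% of the outcome variance, and τ = 10 is 100/5625 = 1.8%.

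**Step 3. Simulation.** The formula is on the minute scale. Two simulations with gamma outcomes and 72 hospital-months gave independent-patient rejection rates of 5.2%, 13.2% and 27.3% (600 runs) and 4.7%, 9.9% and 24.7% (1,500 runs) for τ = 0, 5 and 10. Clustering on hospital-month gave 6.2%, 6.2% and 5.8%, and 6.1%, 5.2% and 5.5%.

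**Step 4. The result depends on how long shocks last.** Independent two-week shocks (26 per period) of SD 5, 10 and 20 minutes give 7.9%, 16.2% and 37% by the same reasoning. At the other extreme, a shock lasting a whole period adds 3τ² (2τ² from the treated hospital, τ² from the mean of two controls). With τ = 2 the true SE is √(3.45² + 12) = 4.89 and type I error is 16.6%.

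**Step 5. What clustering does not repair.** When monthly shocks are serially correlated, clustering on hospital-month still rejects too often in simulation:

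| Autocorrelation | τ = 5 | τ = 10 |
|---|---|---|
| 0.5 | 12% | 19% |
| 0.8 | 24% | 37% |

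For a period-long shock of SD 2, clustering on hospital and two-week period also gave 16.6%.

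**Step 6. Shocks common to all three EDs.** Common monthly shocks of SD 10 (1,000 runs) gave 4.9% with the independent-patient standard error, because they cancel in the difference. Hospital-month clustering without calendar-period effects gave 0.2%: it counts the common part as error.

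**The case against.** **The SAP is silent rather than wrong.** It gives a mean model and names no variance estimator, so independence is an inference. That is fair, but the default output of the specified model is the independent-patient standard error, and nothing in the plan tells the analyst to use another.

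**The size is assumed.** This stands. At an SD of 1 to 3 minutes the test runs at 5% to 7%, a small departure. A reader might infer that the documents themselves reveal the hospital-month variance, because the stated 16-minute detectable effect is larger than the 11.2 minutes its inputs imply. They do not: Step 1 shows that half the sample with independent patients gives the same figure, and the protocol leaves the simulation details to be requested.

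**Shared secular change is what the control hospitals are for.** This stands. Pandemic waves or policy changes that move all three EDs together largely cancel. Only hospital-specific movement inflates the error.

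**Repeat visits are handled.** This also stands. The cohort table excludes later sepsis visits within an analysis window from the primary cohort, so repeat visits are not part of the problem.

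**There are other safeguards.** The SAP plans a parallel-trends test, propensity weights if that test fails (these include SARS-CoV-2 result), and an interrupted time series that lets trends differ by group. All three address bias. None adds hospital-by-time variance to the standard error of β3, and the SAP itself notes that the trends test looks only at the pre-period.

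**This is a phase 2a study of preliminary effects.** True, and it bears on how strongly the conclusion should be worded. It does not justify a fixed significance rule whose error rate is unknown.

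**Conclusion.** The point holds. The primary rule rests on a patient-level model for one treated and two control hospitals with no provision for hospital-specific variation over time. Fitted as written, its standard error is too small whenever such variation exists. How much too small cannot be read from the documents. With independent hospital-month shocks of SD 1 to 10 minutes, true type I error runs from about 5% to about 27%, and it is higher if shocks persist over months.

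Two stronger readings are not supported. One is that the error rate is known to be badly inflated: at the low end of the range it is barely affected. The other is that clustered standard errors would restore 5%: that holds when shocks are independent between clusters, but not when they are serially correlated or last the whole post period. With a single treated hospital, no choice of standard error separates a shock lasting the whole post period from the intervention.

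**What to change.** In the SAP's Data analysis section:

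1. State that the standard error, confidence interval and p-value for β3 are cluster-robust at hospital-by-month level, or hospital by the two-week periods already used in the interrupted time series, with small-sample degrees of freedom.
2. Put hospital and calendar-period effects in the model, so that shocks common to all EDs are not counted as error.
3. State that this only partly repairs the error rate if hospital shocks are serially correlated, and that a shock spanning the post period at the intervention ED cannot be distinguished from Code Sepsis.
4. Reword the decision rule so that a significant β3 alone is not taken as proof of impact.

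The cost is SAP wording and a modest change to the model; no new data are needed. The interval widens: SE about 4.3 at a monthly SD of 5 and 6.1 at 10, against 3.5. Power at the stated 16 minutes becomes about 96% and 75% respectively. For the 36-minute effect implied by the protocol's assumptions (30% activation × (170 − 50) minutes), power stays near 100%.

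### If the parallel-trends pre-test fails, the primary analysis only adds covariate weights, so a residual hospital-specific trend stays in β3, and the time series meant to handle it lacks a hospital term

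*SAP*

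**What the plan says.** The primary estimate is β3, the interaction of intervention hospital and post period in a covariate-adjusted gamma difference-in-differences (DID) model. Impact is declared if β3 is statistically significant (SAP, Data analysis).

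Of the parallel-trends check, the same section says: "This approach allows for testing the parallel trend assumption after conditioning on covariates". It notes that the check uses the pre-implementation phase only. If the check fails: "If the pre-test of parallel trends assumption fails, then we will weight the gamma regression model with propensity scores". The weights are described as balancing observed covariates over the four hospital-by-period groups. No other change to the primary estimate, or to the rule for declaring impact, follows a failure.

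Separately, SAP, Sensitivity analyses, plans a multi-group interrupted time series as the key sensitivity analysis. It is performed whatever the pre-test shows. Of this model it says: "This model allows for the trends to differ between the intervention and control hospitals during the pre-intervention phase". Its equation contains Time, Time by Int, Post, Int by Post and covariates. It has no Int term on its own, although the DID equation does. Nothing says that this estimate replaces the primary one.

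**The concern.** The remedy does not match the failure that it answers. If trends still differ after conditioning on covariates, the likely cause is something that those covariates do not carry, such as a change in staffing or process at one hospital. Weights that equalise case mix across four groups contain no time trend and leave such a cause in place. The study would then report a weighted version of the same contrast as its primary result.

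A differential trend of one sign would be credited to Code Sepsis, and one of the other sign would hide a real effect. The model that does address differing trends has no formal role in the conclusion, and as written it has a fault of its own.

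**Working it through.** **Inputs.** SAP, Power: "the intervention ED provides care for 1,650 sepsis patients annually"; "the control EDs together care for a total of 2,200 sepsis patients annually"; door-to-antibiotic time "average 170 (±75) minutes based on 2013-2017 data from study hospitals". SAP, Data analysis: "Statistical significance will be set to p < 0.05", taken as two-sided. Protocol 4.2.5: a 12-month pre phase, a 3-month roll-in and a 12-month post phase, so the phase midpoints are 15 months apart. Protocol 7.3: 30% activation, and 50 min to antibiotics under the protocol. Assumptions: independent patients, even accrual, linear trends on the minutes scale (the SAP does not state the gamma link), and a pre-test that acts like a test of slope difference (the SAP does not state its period structure).

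**The plan's own figure.** The SAP states: "we estimated 90% power to detect a difference-in-differences change of 16 minutes or more in door-to-antibiotic time". From its inputs:

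- DID SE = sqrt(2×75²/1650 + 2×75²/2200) = sqrt(6.82 + 5.11) = 3.45 min.
- Power at 16 min = Φ(16/3.45 − 1.96) = 99.6%.
- Change detectable with 90% power = 3.24 × 3.45 = 11.2 min.

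The simple formula does not reproduce 90% at 16 min. The stated figure is conservative by comparison, and the simulation details are not given. The 16 min is used below only as the plan's benchmark.

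**Bias from a residual trend.** Bias in β3 = slope difference × 15 months. The last column is the chance of declaring an impact when the protocol has none, with SE 3.45.

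| Slope difference (min/month) | Bias (min) | Impact declared with no effect |
|---|---|---|
| 0.5 | 7.5 | 58% |
| 1.0 | 15 | 99% |
| 1.07 | 16 | over 99% |

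**What weighting does.** A simulation (150 runs, 7,700 patients, gamma outcome, weights to the intervention-hospital post group) compared two sources of a trend of this size. With a calendar trend unrelated to covariates, the bias was 16.3 min unweighted and 16.2 min weighted. With drift in a measured, weighted covariate, it was 15.9 min unweighted and −0.05 min weighted.

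**Strength of the pre-test.** Arrival times spread evenly over 12 months have variance 12²/12 = 12.

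- Slope-difference SE = sqrt(75²/(1650×12) + 75²/(2200×12)) = sqrt(0.284 + 0.213) = 0.705 min/month.
- Power is 29% at 1 min/month, 33% at 1.07 and 81% at 2.
- The smallest significant estimate is 1.96 × 0.705 = 1.38 min/month, which projects to 20.7 min over 15 months.

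**The time series as written.** Let Time start at 0 and run on through the wash-in, so the pre phase is months 0–12 and the post phase is months 15–27. Suppose the hospitals differ by a constant g min (intervention minus control), with no differential trend and no effect. Without an Int term the gap can be fitted only through Time by Int and Int by Post.

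- Fitted slope = g × E[T] / (E[T²] + Var[T]) = 6g/(48 + 12) = 0.1g, with the first two terms from the pre phase and the variance from the post phase.
- β4 = g − 0.1g × 21 = −1.1g, where month 21 is the post-phase midpoint.
- A gap of 10 min gives −11 min, and 20 min gives −22 min.

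The least-squares fit on the full design gives the same values. With Int added, the bias is zero in every linear case checked, including a 10-min gap together with a slope of 1.07 min/month.

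**Price of the corrected time series.** From the design matrix with Int, the SE of β4 is 8.24 min.

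- Power at 16 min = Φ(16/8.24 − 1.96), about 50%.
- Change detectable with 90% power = 3.24 × 8.24 = 26.7 min.
- The effect implied by Protocol 7.3 is 0.30 × (170 − 50) = 36 min, with power Φ(36/8.24 − 1.96) = 99%.

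**The case against.** The strongest reply is that weighting is not an empty remedy. The propensity list adds items that the outcome model lacks: heart rate, respiratory rate, night and weekend arrival, SARS-CoV-2 result, insurance and lactate. The SAP does not say which list the pre-test conditions on. If it uses the shorter one, a failure might come from drift in an added item, and weighting would then remove the trend. This stands. A reader might infer that weighting can never remove a differential trend, and the documents do not support that.

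A reader might also infer that the fallback operates exactly when the DID estimate is biased. It does not. The test would fail about 5% of the time with no trend, and at 1 min/month it would miss the trend about 71% of the time. Those misses are a weakness of the pre-test rather than of the fallback. They are why the time-series result is needed whatever the test shows.

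It can fairly be said that the plan already has a trend-based analysis and performs it unconditionally, so the gap is narrower than an absence. What is missing is its role after a failure and one term in its equation. Promoting it also exchanges one assumption for another, namely linear extrapolation from 12 pre-intervention months.

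Finally, one might argue that the SARS-CoV-2 item cannot be balanced across the four groups. The documents state neither when testing began nor which group the weights target, so this point is not relied on.

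**Conclusion.** The concern holds in a limited form. After a failed pre-test, the primary analysis does not model a residual hospital-specific trend, and any such trend enters β3 in full. The bias is 15 min for each 1 min/month of slope difference and reaches the 16-min benchmark at about 1.07 min/month.

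It would go too far to say that the fallback will leave a bias as large as the effect sought. The documents give no trend size, the figures assume a linear trend that continues through the wash-in and post phases, and the effect implied by Protocol 7.3 is 36 min rather than 16. A slope estimate just large enough to fail the pre-test would project to about 21 min, so a bias of that order is plausible but not established.

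The missing Int term is a definite fault in the sensitivity equation as written. It matters whenever the hospitals differ in baseline level, with or without a differential trend.

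**What to change.** 1. Add the Int main effect to the segmented-regression equation in SAP, Sensitivity analyses.
2. State in SAP, Data analysis, that if the pre-test fails, the corrected time-series estimate is the main basis for the conclusion and the propensity-weighted DID is a sensitivity analysis.
3. Report the time-series estimate and its interval beside the DID result whatever the pre-test shows.

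It would also help to say which covariate list the pre-test conditions on.

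The change is to SAP wording and one model term, and needs no new data. The price is a less precise estimate and reliance on linear extrapolation when the fallback is used. The SAP should state the reduced power for 16 min openly.

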#### 4.2.5 Study phase dates

ED patients arriving to study EDs will be assigned to a study phase based on their ED arrival date.

- *Phase #1* (pre-intervention analysis phase): November 13, 2018 to November 12, 2019
- *Phase #2* (intervention roll-in): November 13, 2019 to February 12, 2020
- *Phase #3* (full intervention analysis phase): February 13, 2020 to February 12, 2021

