#### Study phases and associated exposures

Dhaca	Detient CD envivel deter	Care received by patients		
Phase	Patient ED arrival dates		Intervention EDs	
Pre-intervention analysis	11/13/2018-11/12/2019	Standard care	Standard care	
Post-intervention wash-in	11/13/2019-2/12/2020	Standard care	Code Sepsis protocol	
Post-intervention analysis	2/13/2020-2/12/2021	Standard care	Code Sepsis protocol	

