#### Primary and secondary outcome analysis covariates

Variables listed below will be included in multivariable adjusted analyses for primary and secondary outcomes listed above. Variables are also included in any associated subgroup and sensitivity analyses for these outcomes. For heterogeneity of treatment effect analyses, where continuous variables are categorized or dichotomized, the corresponding adjustment variable will also be categorized analogously in the adjustment model and for creation of the interaction term.

- Age (age, continuous)
- Female sex (sex, binary)
- Presentation from a long-term care facility (snf, binary)
- Weighted Elixhauser comorbidity score (elixhauser\_vw, continuous)
- Arrival to ED via ambulance (arrival\_mode, binary)
- English is preferred language (english\_preferred\_yn, binary)
- First-available temperature in ED (vs\_temp\_cat, categorical, reference group = 1 [temp 36-38°C])
- First-available systolic blood pressure in ED (**vs\_sbp**, continuous)
- Acute physiology score (aps\_24h, continuous)
- ED SOFA score (**sofa\_ed**, continuous)

• ED-diagnosed infection source (**source\_ed\_final\_simpler**, categorical, reference group = 1 [pneumonia])

**Figure 2.** Adjustment variables for primary & secondary multivariable analyses. The primary exposure is intervention ED arrival post-intervention and the primary outcome is door-to-antibiotic time. White symbols indicate potential confounders or precision variables included in the multivariable model, gray symbols represent an unobserved variable, and blue symbols (other than the outcome) represent an ancestor of outcome not included in the multivariable model.

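### If the parallel-trends pre-test fails, the fallback propensity weights cannot deliver the stated four-group balance on SARS-CoV-2 test result unless tested post-period patients get zero weight

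*SAP*

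**What the plan says.** The SAP's Data analysis section makes the weighting conditional: "If the pre-test of parallel trends assumption fails, then we will weight the gamma regression model with propensity scores". It says of the weights that "this will balance the covariates amongst the four study groups defined by their treatment status as well as time (pre vs post"). The list of propensity covariates includes "SARS-CoV-2 test result (positive, negative, or not performed during ED-associated hospitalization or within 14 days preceding ED arrival"), a variable with three levels. For the sepsis cohort the list is only extended ("For analyses involving a cohort of patients with sepsis, propensity score covariates will additionally include arrival to ED via ambulance"), so test result is also in the weights for the primary outcome.

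The dates come from two places that agree. The SAP's phase table gives "11/13/2018-11/12/2019" for the pre-intervention period, and Protocol 4.2.5 gives "November 13, 2018 to November 12, 2019". Both start the post-intervention period on 13 February 2020. The months between supply no patients: "Data from the wash-in phase will be excluded from DID analyses".

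The SAP text names no target population for the weights and no check of overlap or balance. The outcome-model covariates are listed separately ("Variables listed below will be included in multivariable adjusted analyses for primary and secondary outcomes listed above"). SARS-CoV-2 status is not in that list, nor in the one for safety outcomes, so the fallback weights are the only place where the SAP adjusts for it.

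**The concern.** Reweighting changes how much each patient in a group counts. It cannot supply a kind of patient the group does not contain. If no pre-period patient has a SARS-CoV-2 result, the weighted tested share of both pre-period groups is zero whatever the software does, and the four groups can agree only if it is zero in the post-period groups too.

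Once triggered, the fallback supplies the primary-outcome estimate. What happens then depends on a target the SAP text does not state. With a pooled target, the stated balance would not exist and untested post-period patients would carry inflated weights. With a pre-group target, the balance would exist, but the estimate would apply to untested post-period patients only. Nothing in the SAP requires the report to show which of these occurred.

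**Working it through.** **Inputs.** 1,650 intervention and 2,200 control sepsis patients per year and an SD of 75 minutes (SAP, Power). The share of post-period patients tested is not in the documents; 20% to 80% is assumed. Only this covariate is considered, and no pre-period patient is taken to be tested.

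**Step 1, feasibility.** The weighted tested share in each pre-period group is 0 for any non-negative weights. A linear-programming check over four groups and three test levels, at tested shares from 10% to 90%, found a pooled target infeasible every time. The largest tested share that all four groups can have in common was 0.

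**Step 2, formulas.** Let p be the tested share in a post-period group of size n, and s its tested share after weighting.

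- Effective size of that group: n / [s²/p + (1−s)²/(1−p)].
- Standard error (SE) of the contrast: 75 × √(1/1650 + 1/2200 + 1/n_I + 1/n_C), where n_I and n_C are the effective sizes of the intervention and control post-period groups. Unweighted, this is 3.45 minutes.
- Pooled target with equal testing at both sites: s = p/2. The remaining between-period standardised difference is s/√(s(1−s)/2); unweighted it is p/√(p(1−p)/2).
- Pre-group target: s = 0, so n(1−p) patients remain.

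At p = 0.20, for example, the pooled target gives 0.10/√0.045 = 0.47, against 0.20/√0.08 = 0.71 unweighted.

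| Tested | Std. difference, unweighted | Std. difference, pooled target | SE multiplier, pooled | Post patients kept, pre-group target (intervention / control) | SE multiplier, pre-group |
|---|---|---|---|---|---|
| 20% | 0.71 | 0.47 | 1.02 | 1,320 / 1,760 | 1.06 |
| 50% | 1.41 | 0.82 | 1.06 | 825 / 1,100 | 1.22 |
| 70% | 2.16 | 1.04 | 1.14 | 495 / 660 | 1.47 |
| 80% | 2.83 | 1.15 | 1.22 | 330 / 440 | 1.73 |

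**Step 3, unequal testing.** Assume 70% tested at the intervention site and 50% at the controls, a gap of 0.20. Tested patients number 0.7 × 1,650 + 0.5 × 2,200 = 2,255.

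- Pooled four-group target: s = 2,255/7,700 = 0.293 in both post-period groups. Effective sizes are 922 and 1,878, the SE multiplier is 1.12, and a between-period standardised difference of 0.91 remains.
- Pre-group target: s = 0 in both, 495 and 1,100 patients kept, SE multiplier 1.37.
- Balancing the two post-period groups with each other only: s = 2,255/3,850 = 0.586 in both. Effective sizes are 1,553 and 2,137, and the SE multiplier is 1.01.

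All three remove the site gap. The third does so at almost no cost in precision.

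**Step 4, if a few pre-period patients were tested.** The test window covers the ED-associated hospitalisation, so a very long stay could in principle produce a result. Suppose m of the 1,650 pre-period intervention patients were tested and the pooled target share is t/2. Each tested patient then needs weight (t/2)/m and each untested one (1−t/2)/(1650−m). With m = 1 and t from 30% to 90%, the tested patient needs about 290 to 1,350 times the weight of an untested one, and the group's effective size falls to about 44 to 5. With m = 16 it falls to about 541 to 78. Balance becomes possible on paper but is not usable.

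**The case against.** The strongest reply is that the covariate does useful work where it stands. Under a pooled target it shrinks the between-period imbalance (for example from 2.16 to 1.04 at 70% tested), and under either target it equalises the two post-period groups. That second effect matters most for β3: the Post term absorbs a shift in testing shared by both sites, but not a gap between sites after implementation. Simply deleting the variable would lose that adjustment. This stands, and it shapes the fix.

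It is also fair that the fallback is contingent, that the SAP already plans an interrupted time series for non-parallel trends, and that the cited weighting method may fix a target. The cited source is not available here, so which of the two consequences would apply cannot be settled. The feasibility result holds under both.

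Three stronger inferences are not supported:

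- A reader might infer that β3 is biased. Nothing in the documents shows this: with similar testing at both sites the leftover difference is between periods, and with unequal testing either target still equalises the post-period groups.
- A reader might look for the tested share at which power falls below the planned 90%. The simple formula gives 99.6% unweighted for 16 minutes and does not reproduce the SAP's simulated 90%, so no such threshold can be read from it.
- A reader might want a run without SARS-CoV-2-positive encounters. That would not address the lack of overlap.

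**Conclusion.** The concern holds for the fallback analysis. The SAP attributes to its weights a balance that the design cannot give for one listed covariate, except by setting aside every tested post-period patient. The feasibility result rests on one assumption: that no, or almost no, patient arriving by 12 November 2019 has a SARS-CoV-2 result. The sizes in the table also rest on assumed testing shares and on this covariate acting alone; other weights would add variance. What is at stake is an incorrect balance statement or an undisclosed narrowing of the population, with some loss of precision. The SAP should be changed before the fallback is used.

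**What to change.** In the SAP's Data analysis section:

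1. Take SARS-CoV-2 test result out of the four-group propensity model. In the main fallback weights, balance it between the two post-period groups only, where overlap exists, so that adjustment for a between-site difference is kept.
2. Limit the four-group balance statement to the remaining covariates, and state the weight target.
3. Report covariate balance and effective sample size for each of the four groups.

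The cost is a few sentences and one added balancing step on a variable already planned. There are two downsides. The between-period difference in testing is left to the Post term, and test status may be established after arrival. For the second reason, a run without the SARS-CoV-2 weights should be shown beside the main fallback result. Both runs are needed only if the pre-test fails. The unweighted primary model and the interrupted time series stay as they are.
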